Table 4	Criteria for Potentially Clinically Important Laboratory Tests	38		
Table 5	Normal Range of Pulse Rate (beats/min)	39		
Table 6	95th Percentile Cut-off Values of Blood Pressure Norms by Sex, Age, and Height Percentiles	40		
Table 7	Criteria for Potentially Clinically Important ECG Values	41		
	LIST OF IN-TEXT FIGURES			
Figure 1	Study Design Flow Chart	8		

Page 6

Version 2.0/16 Aug 2018

ABBREVIATIONS

ADHD attention-deficit/hyperactivity disorder

Attention-deficit/Hyperactivity Disorder Rating Scale-5 ADHD-RS-5

adverse event AΕ

Shire

Protocol SHP465-309

ANCOVA Analysis of covariance BMI body mass index

CGI-I Clinical Global Impressions-Improvement CGI-S Clinical Global Impressions–Severity of Illness

CI confidence interval

CMH Cochran-Mantel-Haenszel **CRO** contract research organization

C-SSRS Columbia-Suicide Severity Rating Scale Children's Sleep Habits Ouestionnaire **CSHO**

date of informed consent **DINFC**

DOB date of birth

DSM-5 Diagnostic and Statistical Manual of Mental Disorders, Fifth Edition

ECG electrocardiogram

electronic case report form eCRF

ET early termination **FAS** full analysis set

FDA Food and Drug Administration **FoTA** Final on-Treatment Assessment **IWRS** interactive web response system

missing at random MAR

MCH mean corpuscular hemoglobin

MCHC mean corpuscular hemoglobin concentration

MCV mean corpuscular volume

MedDRA Medical Dictionary for Regulatory Activities

MINI-KID Mini International Neuropsychiatric Interview for Children and Adolescents

MMRM mixed-effects model for repeated measures

MNAR missing not at random

PCI potentially clinically important **PSO** Post Sleep Questionnaire QT QT interval of the cardiac cycle

QTcB Bazett's corrected QT interval OTcF Fridericia's corrected OT interval

RBC red blood cells

REML restricted maximum likelihood

SAE serious adverse event SAP statistical analysis plan SD standard deviation SOC system organ class

TEAE treatment-emergent adverse event

US United States **WBC** white blood cells

WHO World Health Organization

1. INTRODUCTION

This statistical analysis plan (SAP) provides a technical and detailed elaboration of the statistical analyses of efficacy and safety data as described in the protocol dated 07 September 2017, the protocol administrative change #1 dated 20 Oct 2017, and the protocol administrative change #2 dated 28 Nov 2017. Specifications for tables, figures, and listings are contained in a separate document.

2. STUDY DESIGN

2.1 General Study Design

This study is a Phase 3 randomized, double-blind, multi-center, parallel-group, placebo-controlled, fixed-dose, efficacy, and safety study in which children aged 6-12 with attention-deficit/hyperactivity disorder (ADHD) will be randomized at baseline (Visit 2) in a 1:1 ratio to SHP465 6.25 mg or placebo for 4 weeks of double-blind treatment as outlined in Table 1.

[figure not shown]
The study will have up to 3 periods as outlined below and in Figure 1:

- Screening and washout period (up to 32 days)
- Treatment period (4 weeks)
- Safety follow-up period (1 week)

Approximately 60 subjects will be randomized in this study to evaluate the efficacy and safety of SHP465 6.25 mg, administered as a daily morning dose in the treatment of children aged 6-12 years with ADHD. Approximately 50% of the total number of subjects will be aged 6-8 years and approximately 50% of subjects will be aged 9-12 years. Approximately 25% of all subjects will be female.

This study will be conducted at approximately 45 sites in the United States (US).

Figure 1 Study Design Flow Chart

ET=early termination; V=visit; W=week

2.2 Randomization

Protocol SHP465-309

Shire

Subject numbers are assigned to all subjects as they consent to take part in the study. Within each site (numbered uniquely within a protocol), this number is assigned to subjects according to the sequence of presentation for study participation.

The actual treatment given to individual subjects is determined by a randomization schedule. Subjects who meet all inclusion criteria and none of the exclusion criteria will be randomized in a 1:1 ratio to either SHP465 6.25 mg or placebo. Randomization will be stratified to ensure approximately 50% of subjects in each age group (6-8 years and 9-12 years), and to facilitate balance of treatment allocation within each age group. The study is not powered to detect within age stratum treatment effects.

The randomization number represents a unique number corresponding to investigational product allocated to the subject, once eligibility has been determined. Individual subject treatment is automatically assigned by the interactive web response system (IWRS).

Investigational product packaging identification numbers, separate from randomization numbers/unique identifiers, may also be assigned to subjects for specific treatment assignment as dictated by the study. In these cases, the same investigational product packing identification number may not be assigned to more than 1 subject.

2.3 **Blinding**

This is a double-blind, placebo-controlled study. All investigational and reference product (SHP465 6.25 mg or placebo) will appear identical to protect the study blind.

Data that may potentially unblind the treatment assignment (i.e., treatment allocation, and investigational product preparation/accountability data) will be handled with special care during the data cleaning and review process. These data will be handled in such a way that, prior to unblinding, any data that may unblind study team personnel will be presented as blinded information or otherwise will not be made available. If applicable, unblinded data may be made available to quality assurance representatives for the purposes of conducting independent drug audits.

The treatment assignment must not be broken during the study except in emergency situations where the identification of the investigational product is required for further treatment of the subject. The investigator should contact the medical monitor as soon as possible after the investigator has been unblinded.

In the event that the treatment assignment is broken, the date, the signature of the person who broke the code and the reason for breaking the code will be recorded on the IWRS and the source documents. Upon breaking the blind, the subject will be withdrawn from the study but should be followed up for safety purposes. Any code breaks that occur must be reported to the contract research organization (CRO) and to Shire. Code-break information is held by the pharmacist/designated person at the site and by the CRO medical monitor/designated person for

the study. There will be a provision for unblinding to ensure adequate treatment of the subject in the case of an emergency.

2.4 Schedule of Assessments

Table 1 below presents a schedule of study assessments.

Table 1 Schedule of Assessments

	Screening/Washout ^a		Baseline	Treatment Period				Follow-up
Visit Number ^b	1	Phone call	2	3	4	5	6/ET ^c	Phone call
Study Week	-5 to -1	-1	0	1	2	3	4	5
Study Day ^b	-32 to −3	-7	0	7	14	21	28	35
Informed consent/assent	✓							
Inclusion/exclusion criteria	✓	√d	√d					
Subject demography	✓							
MINI-Kid	✓							
Medical history ^e includes prior medications and procedures	✓							
Randomization			✓					
ADHD-RS-5 ^f			✓	✓	✓	✓	✓	
CGI-S ^f			✓					
CGI-I ^f				✓	✓	✓	✓	
Urine drug screen	✓		√g					
Serum pregnancy test ^k	✓		√g					
Urine pregnancy test ^k			✓				✓	
Physical examination	✓		√g					
Height ^h	✓		✓	✓	✓	✓	✓	
Weight ^h	✓		✓	✓	✓	✓	✓	3
Vital signs ^{i,j}	✓		√	✓	✓	✓	✓	
Clinical laboratory test	✓		√g				✓	
Electrocardiogram (12-lead) ^l	√ ⁱ		√g,i		✓		✓	
C-SSRS baseline version	✓							
C-SSRS since last visit version			✓	✓	✓	✓	✓	
PSQ ^f			✓	✓	✓	✓	✓	
CSHQ ^f		2	✓	✓	✓	✓	✓	
Adverse events	√	✓	✓	✓	✓	✓	✓	✓
Concomitant medications	1	✓	√	✓	✓	✓	✓	✓

Table 1 Schedule of Assessments

	Screening/Washout ^a		Baseline	Treatment Period				Follow-up
Visit Number ^b	1	Phone call	2	3	4	5	6/ET ^c	Phone call
Study Week	-5 to -1	-1	0	1	2	3	4	5
Study Day ^b	-32 to -3	-7	0	7	14	21	28	35
Subject check to remain in study ^f			✓	✓	✓	✓		
IWRS	✓		√	✓	✓	✓	✓	
Study drug dispensed			✓	✓	✓	✓		
Study drug capsules returned	1		8	✓	✓	✓	✓	

ADHD-RS-5=Attention-deficit/Hyperactivity disorder-Rating Scale 5 Child, Home Version; BMI=body mass index; CGI=Clinician's Global Impression; C-SSRS=Columbia-Suicide Severity Rating Scale; ET=early termination; IWRS=interactive web response system; MINI=Mini International Neuropsychiatric Interview (MINI) Kid version for Children and Adolescents; PSQ=Post Sleep Questionnaire; CSHQ=Children's Sleep Habits Questionnaire.

- Following successful screening, a site representative will contact the subject's parent/LAR to instruct the subject on discontinuing any prohibited medication for the washout period.
- b Visit windows are with respect to baseline (Visit 2) and ±2 days during the treatment period and +2 days for the safety follow-up phone call.
- Subjects who terminate early will undergo the evaluations listed for Visit 6.
- d Inclusion/exclusion criteria will be reviewed during the washout phone call and at baseline (Visit 2).
- Medical history will include all lifetime psychiatric and nonpsychiatric medications and procedures.
- Whenever possible, the same individual should complete/rate consistently the following scales and questionnaires as appropriate: ADHD-RS-5, CGI-S/I, and subject check to remain in the study; and the same caregiver/LAR for PSQ and CSHQ. Include assessment of decreased appetite.
- If > 32 days have elapsed since the screening evaluation was completed at Visit 1, then the following evaluations must be repeated at baseline (Visit 2): vital signs, serum pregnancy test, urine drug screen, clinical laboratory evaluations, and ECGs in triplicate. The physical exam will be abbreviated with a review of the following body systems: general appearance, respiratory, and cardiovascular.
- h Height and weight will be measured without shoes and with light clothing using a calibrated stadiometer for height and calibrated scale for weight.
- Vital signs include oral or tympanic temperature, pulse, sitting blood pressure, and respiration rate. The subject will have been seated for a minimum of 3 minutes before blood pressure, pulse and respiration rate measurements are taken. Measurement of blood pressure and pulse will be collected 3 times (with approximately 2 minutes in between each collection). The average of each set of 3 measurements will be used to determine continued participation in the study.
- Blood pressure and pulse rate will be measured at each study visit. Temperature and respiration rate will be measured at screening (Visit 1) and/or baseline (Visit 2) only.
- ^k For females of child-bearing potential only.
- Electrocardiograms will be recorded in triplicate with approximately 3 minutes in between each collection at screening only and at baseline only if >32 days have elapsed since the screening evaluation was completed at Visit 1.

2.5 Determination of Sample Size

The primary efficacy endpoint is defined as the change from baseline in the Attention-deficit/Hyperactivity Disorder Rating Scale Version 5 (ADHD-RS-5) total score at Visit 6 (Week 4). The baseline ADHD-RS-5 total score is the last value obtained prior to taking the first dose of investigational product, usually at Visit 2.

The null hypothesis is that there is no difference in mean change from baseline at Visit 6 (Week 4) in ADHD-RS-5 total score between SHP465 6.25 mg and placebo, and the alternate hypothesis is that there is a difference in mean change from baseline at Visit 6 (Week 4) in ADHD-RS-5 total score between SHP465 6.25 mg and placebo.

The sample size was estimated for the primary comparison of SHP465 at 6.25 mg with placebo by using nQuery Advisor 7.0. To detect an assumed difference of 11.9 for the change from baseline in the ADHD-RS-5 total score between the SHP465 at 6.25 mg treatment group and the placebo group with the assumed common standard deviation (SD) of 14, 26 completers per group are needed to provide 85% power for a 2-sided t-test with α level of 0.05. This yields a total of 52 subjects (26 on active treatment and 26 on placebo). Taking into account an expected post-randomization dropout rate of 15%, the randomization target is set at 60 subjects in total.

The assumptions of a treatment difference of 11.9 and a standard deviation of 14.0 corresponds to an effect size of 0.85 which is low compared with that in recently completed study (SHP465-305) of children and adolescents aged 6-17 years with ADHD treated with SHP465. The SHP465-305 study yielded an effect size of 0.93 in children aged 6-12 years (101 subjects).

A blinded interim analysis at the late stage of the trial (when approximately 75% of all randomized patients have either completed or discontinued from the study) is needed for a possible sample size increase in case of an underestimated variability postulated at the design stage (see Section 15).

The final total number of subjects randomized between the 2 groups will be calculated in the blinded interim analysis, based on the estimate of the pooled variance, as detailed in Section 15. The number of subjects could remain at 60, or could potentially be as high as 90, which corresponds to the 97.5th percentile of the distribution of the variance estimator based on the true standard deviation of 14.0. Note that the total of 90 subjects is not considered a cap. As the final sample size is data driven, a higher number, though unlikely, is possible.

2.5.1 Sample Size Update

Following the SAP Section 2.5 and the protocol Section 9.6, a blinded interim analysis for sample size re-estimation was performed based on 47 randomized subjects as of 19 March 2018 (the interim cohort), among which 45 were in the FAS and 43 completed the study. Data of the interim cohort were extracted on 27 April 2018, after the collection of all their primary efficacy data.

The pooled standard deviation for Visit 6 (Week 4) used for sample size re-estimation was calculated using a pooled common variance that was estimated by using blinded cumulative primary efficacy data in the interim cohort. Then the final pooled standard deviation was

calculated as stated in Section 15 and Appendix 1. The interim analysis results showed a reestimated pooled standard deviation of 13.29 which is less than 14 and therefore an increase to the sample size was not required.

2.6 Multiplicity Adjustments for Type I Error Control

In order to protect the study-wide Type I error at the 2-sided 0.05 for testing across the primary and the key secondary hypotheses, the Fixed-Sequence Test procedure will be used (see Section 11 for details).

3. OBJECTIVES

3.1 Primary Objective

The primary objective of this study is to evaluate the efficacy of SHP465 at 6.25 mg compared to placebo as a daily morning dose in children 6-12 years of age (inclusive at the time of consent) diagnosed with ADHD. The primary measure of efficacy will be the clinician-administered ADHD-RS-5 Child Home Version total score.

3.2 Secondary Objectives

Key Secondary:

• To assess the efficacy of SHP465 at 6.25 mg compared to placebo using a global clinical measure of improvement, the Clinical Global Impression of Improvement (CGI-I) scale.

Secondary:

• To evaluate the safety and tolerability of SHP465 at 6.25 mg based on the occurrence of treatment-emergent adverse events (TEAEs), evaluation of vital signs (systolic and diastolic blood pressure and pulse), weight, height, body mass index (BMI), clinical laboratory and electrocardiogram (ECG) results, sleep assessment (Post Sleep Questionnaire [PSQ] and Child's Sleep Habits Questionnaire [CSHQ]), and responses to the Columbia Suicide Severity Rating Scale (C-SSRS).

4. ESTIMANDS

4.1 Primary Estimand

The primary estimand is the mean change from baseline to Week 4 in ADHD-RS-5 total score between active (SHP465 6.25 mg) and placebo groups.

- Population: 6-12 year old children with ADHD defined through inclusion and exclusion criteria as stated in the protocol
- Variable: change from baseline to Week 4 in ADHD-RS-5 total score
- Intercurrent event: had patients not discontinued treatment
- Population-level summary: difference in mean change of ADHD-RS-5 total score from baseline to Week 4 between active (SHP465 6.25 mg) and placebo groups

4.2 Secondary Estimand

The key secondary estimand is the mean CGI-I value at Week 4 between active (SHP465 6.25 mg) and placebo groups.

- Population: 6-12 year old children with ADHD defined through inclusion and exclusion criteria as stated in the protocol
- Variable: CGI-I value at Week 4
- Intercurrent event: had patients not discontinued treatment
- Population-level summary: difference in mean CGI-I value at Week 4 between active (SHP465 6.25 mg) and placebo groups

5. SUBJECT POPULATION SETS

The following subject sets are applicable to this study:

5.1 Screened Set

The Screened Set will consist of all subjects who have provided informed consent.

5.2 Randomized Set

The Randomized Set will consist of all subjects in the Screened Set for whom a randomization number has been assigned.

5.3 Safety Set

The Safety Set will consist of all subjects in the Randomized Set who have taken at least 1 dose of investigational product.

5.4 Full Analysis Set

The Full Analysis Set (FAS) will consist of all subjects in the Safety Set who have had the baseline ADHD-RS-5 total score and at least 1 post-dose ADHD-RS-5 total score.

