4.1 Inclusion Criteria

The subject will not be considered eligible for the study without meeting all of the criteria below (including test results).

- 1. Subject is male or female aged 6-12 years inclusive at the time of consent.
- 2. Subject's parent or LAR must provide signature of informed consent, and there must be documentation of assent (as applicable) by the subject in accordance with the International Council on Harmonisation (ICH) Good Clinical Practice (GCP) Guideline E6 (1996) and any updates and applicable regulations, before completing any study-related procedures.
- 3. Subject and parent/LAR are willing and able to comply with all of the testing and requirements defined in the protocol, including oversight of morning dosing. Specifically, the parent/LAR must be available at approximately 7:00 AM (±2 hours) to dispense the dose of investigational product for the duration of the study.
- 4. Subject must meet Diagnostic and Statistical Manual of Mental Disorders, Fifth Edition (DSM-5) criteria for a primary diagnosis of ADHD (any subtype) based on a detailed psychiatric evaluation using the Mini International Neuropsychiatric Interview version for Children and Adolescents (MINI-KID).
- 5. Subject who is a female and of child-bearing potential must not have a positive serum beta human chorionic gonadotropin pregnancy test at the screening visit (Visit 1) and must have a negative urine pregnancy test at the baseline visit (Visit 2) and agree to comply with any applicable contraceptive requirements of the protocol.
- 6. Subject has an ADHD-RS-5 Child, Home Version Total Score of ≥28 at baseline (Visit 2).
- 7. Subject has a Clinical Global Impression Severity of Illness (CGI-S) score ≥4 at baseline (Visit 2).
- 8. Subject functions as an age-appropriate level intellectually, as determined by the investigator.
- 9. Subject is currently not on ADHD therapy, or is not completely satisfied with their current ADHD therapy.
- 10. Subject has lived with the same parent/LAR for at least 6 months.

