6. SUBJECT DISPOSITION

A listing of all Screen Failures (i.e., subjects who were screened but not randomized) will be presented along with reasons for screen fail and details of any adverse events (AEs).

The number of subjects included in each analysis set (i.e., Screened, Randomized, Safety, FAS) will be summarized by treatment group (SHP465 6.25 mg or Placebo) and overall, except for the Screened Set, which will be summarized only overall.

The number and percentage of subjects who completed and prematurely discontinued during the Treatment period will be presented for each treatment group and overall for the Safety Set. Reasons for premature discontinuation from the Treatment period, as recorded on the end of study discontinuation page of the electronic case report form (eCRF), will be summarized (number and percentage) by treatment group for the Safety Set. The subjects who completed the study are those that completed the final scheduled visit (Visit 6) at the end of the Treatment period.

In addition, the number and percentage of subjects who completed the study visits will be presented by visit for each treatment group and overall for the Safety Set.

All subjects who prematurely discontinued during the Treatment period will be listed by discontinuation reason for the Randomized Set.

Follow-up information, new (post-treatment) AEs and new (post-treatment) medication, will be listed for the Safety Set.

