11. EFFICACY ANALYSES

All efficacy analyses will be performed using the FAS. All statistical tests will be 2-sided hypothesis tests performed at the 0.05 level of significance. All confidence intervals (CI) will be 2-sided 95% CIs, unless stated otherwise. Only post-baseline assessments from Visit 3 (Week 1) up to Visit 6 (Week 4) that were collected on or before 2 days after the last dose of double-blind investigational product will be analyzed.

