11.3 Adjustments for Multiplicity for the Primary and Key Secondary Endpoint

In order to protect the study-wide Type I error at the 2-sided 0.05 for testing across the primary and the key secondary hypotheses, the Fixed-Sequence Test procedure will be applied. The hypotheses will be tested in the order of the primary (ADHD-RS-5 Total Score) and then the secondary (CGI-I), if significant for the primary, each at the 2-sided 0.05 significance level. Both tests in the sequence are based on the MMRM.

11.4 **Sensitivity Analysis Based on Missing Not at Random Assumptions**

The primary efficacy analysis (MMRM) relies on the assumption that the missing data mechanism follows the MAR (missing at random) scenario. It is assumed that the probability of missing data is unrelated to the value of the variable, after controlling for other variables in the data. The likelihood-based MMRM analysis is considered an appropriate method for the statistical analysis under MAR assumptions.

The following 2 sensitivity analysis models will be used to examine robustness of the primary analysis results. The sensitivity analysis models assume different MNAR mechanisms and are within the pattern-mixture model framework.

Model 1 - Placebo multiple imputations

Rationale: The imputations are based on the distribution of placebo group responses over time. The underlying assumption is that a subject on SHP465 6.25 mg treatment with missing data follows the distribution of the placebo responses, i.e., the means and the intra-subject correlations based on the placebo responses will apply.

The model is implemented in 3 steps: 1. imputations, 2. analysis of complete data sets, and 3. inference. Sample SAS codes are provided in Section 22.

Step 1: Imputations

A total of 200 sets of posterior mean and co-variance estimates are extracted from the SAS MI procedure using the available non-missing placebo data. One hundred of the posterior sets will be applied to the SHP465 6.25 mg treatment group, the other 100 applied to the placebo group. One set of imputations for all missing values will be generated based on each variation of posterior estimates. All 100 sets for imputations within a treatment group will be ordered from 1 to 100, and combined between the SHP465 6.25 mg treatment group and placebo, for a total of 100 completely imputed data sets.

Step 2: Analysis of complete data sets

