22.2 Appendix 2 Sample SAS Codes

Mixed Model Repeated Measures (MMRM)

```
Proc mixed /* select derived data set */;
Class trt subjid visit agegp;
Model chg = trt visit agegp trt*visit base base*visit / ddfm=kr;
Repeated visit / subject=subjid type=UN;
/* LSMean, Estimate, and/or LSMestimate statement(s) */
/* Data output or object delivery statement(s) */
Run;
```

Mixed Model Repeated Measures (MMRM) for subgroup analysis

```
Proc mixed /* select derived data set */; Class trt
subjid visit;
Model chg = trt visit trt*visit base base*visit / ddfm=kr; Repeated visit /
subject=subjid type=UN;
by subgroup;
/* LSMean, Estimate, and/or LSMestimate statement(s) */
/* Data output or object delivery statement(s) */
Run;
```

Analysis of Covariance (ANCOVA)

```
Proc glm /* select derived data set */;
Class trt;
Model chg = trt agegp base/alpha=.05;
Lsmeans trt/stderr pdiff;
/* Data output or object delivery statement(s) */
Run;
```

Missing Not at Random (MMNAR) Sensitivity Analysis

Model 1: Placebo Multiple Imputation

```
* Step 1;
proc mi data=unimputed out=discard nimpute=200 seed=309 noprint;
    where treatment=1; * where 1 stands for placebo;
    var baseline chy1-chy4;
    mcmc outest=posteriors; * here we pick up the PLA posteriors;
run;

* 100 posteriors for the placebo, rest for SHP465 6.25 mg;
data posteriors(type=est);
    set posteriors;
```

```
if 1<=_imputation_<=100 then do; * assign placebo posteriors;
              treatment=1;
         end;
        if 100<_imputation_<=200 then do; * assign posteriors to SHP465 6.25 mg;
              treatment=2;
              _imputation_=_imputation_-100;
        end;
 run;
 proc sort data=unimputed;
    by treatment;
 run;
 proc mi data=unimputed out=imputed;
    by treatment;
    var baseline chy1-chy4;
    mcmc inest=posteriors; * here we use the placebo posteriors;
 run;
 * Step 2;
data endpoint;
    set imputed;
    endpoint=chy4;
run;
 proc sort data=endpoint;
    by _imputation_;
 run;
 proc glm data=endpoint;
    by _imputation_;
    class treatment agegp;
    model endpoint = baseline treatment agegp / solution;
    Ismeans treatment;
    estimate 'SHP465 6.25 mg vs placebo' treatment -1 1;
    ods output estimates=est;
 run;
 * Step 3;
 proc sort data=est;
    by label_imputation_;
 run;
 proc mianalyze data=est;
    by label;
    modeleffects estimate;
    stderr stderr;
 run;
```

Protocol SHP465-309

Model 1.

Model 2: Multiple Imputations with Penalties Applied to Dropouts

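### The two missing-not-at-random models leave out randomised children with no post-dose ADHD-RS-5 score, so the check on dropout is incomplete, with an effect whose direction is unknown

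*SAP*

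**What the plan says.** SAP 11 sets the rule: "All efficacy analyses will be performed using the FAS". Protocol 9.9 says the same. SAP 5.4 limits the FAS to children in the Safety Set (at least one dose) "who have had the baseline ADHD-RS-5 total score and at least 1 post-dose ADHD-RS-5 total score".

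SAP 11.4 then introduces Models 1 and 2: "The following 2 sensitivity analysis models will be used to examine robustness of the primary analysis results". Model 1 imputes missing values from the placebo distribution. Model 2 imputes under MAR within arm and then worsens the imputed Week 4 values by a fraction of the SD. SAP 11.5 applies both models to CGI-I. Neither section names another analysis set.

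The imputation code in SAP 22.2 uses "var baseline chy1-chy4" for both models. Age group is absent, although it is the randomisation stratum (SAP 2.2) and a factor in the ANCOVA fitted to the imputed data (SAP 11.4, Step 2).

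SAP 2.5.1 reports the blinded interim, "based on 47 randomized subjects as of 19 March 2018", "among which 45 were in the FAS and 43 completed the study".

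**The concern.** For the primary MMRM the FAS restriction costs nothing, because a child with no post-baseline change score adds nothing to that likelihood. Models 1 and 2 are different: they exist to ask what happens if children who leave do worse than MAR predicts. The children with the most missing data are removed before that question is put.

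The plan's own definitions are wider than the set used. The estimand population in SAP 4.1 is defined by eligibility, and its strategy asks about outcomes had children not discontinued. Model 2's rationale in SAP 11.4 concerns those who drop out, without limiting them to dropouts who have a post-dose score. Outside the FAS, these children appear only in the disposition counts and listings of SAP 6.

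The data needed to include them should exist. A Visit 2 ADHD-RS-5 score of at least 28 is required for entry (Protocol 4.1), and the planned imputation can fill in a record that has baseline only. At stake is how much of the dropout problem the robustness statement covers.

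**Working it through.** **Planning figures.** SAP 2.5 assumes a difference of 11.9, SD 14, two-sided alpha 0.05 and 26 completers per group for 85% power. A two-sample t-test calculation gives 85.2%, so the planning values reproduce. The target is 60 randomised at 1:1, or 30 per arm.

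**Interim counts (SAP 2.5.1).**
- Non-completers: 47 − 43 = 4.
- Outside the FAS: 47 − 45 = 2.
- Non-completers inside the FAS: 45 − 43 = 2, if every completer is in the FAS. This is close to forced: SAP 6 defines completion as completing Visit 6, where the scale is scheduled, and a baseline score is an entry criterion.
- Share of non-completers outside Models 1 and 2: 2/4 = 50%, exact 95% CI 7% to 93%.
- Children whose Week 4 value would be imputed: 2/45 = 4.4% in the FAS, against 4/47 = 8.5% if all randomised children were included.

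**Scaled to 60.** Non-completers: 60 × 4/47 = 5.1. Outside the FAS: 60 × 2/47 = 2.6. If dropout instead reached the planned 15% with half excluded, 60 × 0.15/2 = 4.5 would be outside.

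**Model 1.** An added active child is imputed as placebo-like, so with k_A such children among 30 the loss is 11.9 × k_A/30. An added placebo child is imputed from placebo data and causes no dilution.
- One active child: 11.9/30 = 0.4 points.
- 2.6 children split evenly (1.3 active): 11.9 × 1.3/30 = 0.5 points, leaving about 11.4.
- Three children, all active: 11.9 × 3/30 = 1.2 points, leaving 10.7.
- Five children, all active (the 15% case, rounded up): 11.9 × 5/30 = 2.0 points, leaving 9.9.

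**Model 2.** The code in SAP 22.2 adds the penalty to every missing Week 4 value, whichever the arm. Taking the MAR imputation for an added child as roughly the arm mean, a 1-SD penalty changes the difference by 14 × (k_A − k_P)/30, where a positive value is a loss for active.
- One active child: a loss of 14/30 = 0.47 points.
- One placebo child: a shift of 0.47 points towards active.
- An even split: no net change.
- Three children, all active: a loss of 1.4 points, leaving 10.5.

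**Against the precision of the trial.** The planning standard error is 14 × √(2/26) = 3.88. Holding it fixed, t = 11.9/3.88 = 3.1 at the planned effect, 10.7/3.88 = 2.8 with three excluded active children under Model 1, and 9.9/3.88 = 2.6 with five. The critical value on 50 degrees of freedom is about 2.0.

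**The case against.** The strongest reply is that Models 1 and 2 test the primary result, so they belong on the primary set. Holding the set fixed isolates the missing-data assumption, whereas changing both set and assumption mixes two effects. This stands, and is why the wider run should be an addition rather than a replacement.

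Second, the two children may never have been dosed. Dosing starts the morning after Visit 2 (Protocol 6.2.3), and leaving never-dosed children out of a blinded trial carries little risk of bias. The documents do not settle this. SAP 9.1 cuts the other way: a child lost after Visit 2 is not assumed to have taken product unless there is a post-baseline safety assessment, so a child who was dosed and then vanished could be classed as undosed.

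Third, the gap is narrow. Early leavers should have the Visit 6 evaluations (Protocol 4.4 and 7.1.2.2), and SAP 19.3 assigns that score to the next nominal visit. A dosed child therefore leaves the FAS mainly by missing both Visit 3 and the early-termination rating. SAP 6 also reports the analysis sets by arm and lists discontinuations for the Randomized Set. That allows a reader to bound the effect, but it is not an analysis.

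A reader might go further and infer that the FAS runs will look more robust than they should. The documents do not support that. The interim was blinded, an excluded placebo child dilutes nothing under Model 1, and under Model 2 as coded such a child moves the estimate towards active. Nor do they support a forecast that half of the final dropouts will be excluded: 2 of 4 is too small a count.

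**Conclusion.** The gap is real but modest. As written, no missing-not-at-random analysis covers randomised children who have a baseline score and nothing after it, and at the interim these were 2 of 4 non-completers. At planning values Model 1 on the wider set would lose about 0.5 points if 2.6 excluded children split evenly by arm, and about 1.2 of 11.9 if three were all on active. Model 2 could move either way by about 0.5 points per child at the 1-SD penalty.

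These sizes assume that the interim rate carries to 60, that there are 30 children per arm, and that the arm split is as stated; the split is unknown. They do not show that the primary result would change: even three excluded active children leave t near 2.8 under Model 1. The wider run could alter a robustness conclusion only if the observed effect were much closer to the significance boundary than planned.

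Leaving age group out of the imputation is a smaller inconsistency. With few imputed children its effect should be small, but a baseline-only record has little else to be imputed from.

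**What to change.** - Keep the FAS for the primary MMRM and for the planned runs of Models 1 and 2.
- In SAP 11.4, add one further run of each model on all randomised children with a baseline ADHD-RS-5 score, including those with no post-dose score. Make the parallel addition for CGI-I in SAP 11.5, using baseline CGI-S.
- Add age group, as a numeric indicator, to the imputation variables of both models in SAP 22.2, so that the imputation carries the stratum that the ANCOVA adjusts for.
- Report the children outside the FAS by arm, with the reason and whether they were dosed.
- Record the use of a set other than the FAS in SAP 18, because Protocol 9.9 puts all efficacy analyses on the FAS.

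The cost is a few lines of SAP text, a second input data set, a little more programming and slightly wider intervals in the added runs. The primary analysis is unaffected.
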